Describe the characteristics of the subject population, including age range, gender, ethnic background and health status. Identify the criteria for inclusion and exclusion.

Provide the following information:

- A description of the subject selection criteria and rationale for selection in terms of the scientific objectives and proposed study design;
- A compelling rationale for proposed exclusion of any sex/gender or racial/ethnic group;
- Justification for the inclusion of vulnerable groups such as children, prisoners, adults with impaired consent capacity, or others who may be vulnerable to coercion or undue influence.

Please consider these resources:

- [NIH Diversity Policy](#)
- [FDA Diversity Guidance](#)

This study will include 70 subjects of either gender. Subjects will be randomly assigned to the following groups: (1) normal weight-bearing, massage (WB-M), (2) normal weight bearing, no massage (WB-C) (3) ULLS, no massage (U-C), and (4) ULLS, massage (U-M). Inclusion criteria are as follows: healthy subjects aged 18-30 years. Exclusion criteria include:

- BMI over 27
- Have current lower extremity musculoskeletal injuries
- Have had previous lower extremity surgeries or injury
- Activities of daily living require long periods of standing or driving a manual transmission car.
- Evidence or signs and symptoms of metabolic syndrome or disorder (diagnosis of diabetes or insulin resistance, elevated BP, high fasting blood sugar, abnormal cholesterol or triglyceride levels).
- Thyroid disorder
- Acute or chronic infections
- Use of systemic steroids, anabolic steroids, or growth hormone
- Are currently pregnant
- Have a family history of bleeding problems ("free bleeder"), as evidence by:
 - o unexplained nosebleeds (epistaxis)
 - o excessive or prolonged menstrual blood flow (menorrhagia)
 - o prolonged bleeding after minor cuts, dental procedures, tooth brushing or flossing, or trauma
- Are using medications that increase the risk of bleeding (unless it can be safely stopped):
 - o Aspirin
 - o Clopidogrel
 - o non-steroidal anti-inflammatory drugs
 - o any anticoagulation therapy (warfarin or heparin)
- Are allergic to Betadine or Xylocaine HCl.
- Any other condition or events considered exclusionary by the PI and /or physician, such as non-compliance

Attachments

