Indicate the targeted/planned enrollment of the following members of minority groups and their subpopulations. Possible demographic sources: [Census Regional Analyst Edition](#), [Kentucky Race/Ethnic Table](#), [Kentucky Population Data](#).
(Please note: The IRB will expect this information to be reported at Continuation Review time for Pre-2019 FDA-regulated Expedited review and Full review applications):

| Participant Demographics | | | | |
|---|----------------------|----------------------|----------------------|----------------------|
| | Cisgender Man ⓘ | Cisgender Woman ⓘ | TGNB/TGE ⓘ | Unknown/Not Reported |
| American Indian/Alaskan Native: |  |  |  |  |
| Asian: | 3 | 3 |  |  |
| Black/African American: | 9 | 9 |  |  |
| Latinx: | 2 | 2 |  |  |
| Native Hawaiian/Pacific Islander: |  |  |  |  |
| White: | 56 | 56 |  |  |
| American Arab/Middle Eastern/North African: |  |  |  |  |
| Indigenous People Around |  |  |  |  |

| | | | | |
|--------------------------|--|--|--|--|
| the World: | | | | |
| More than One | | | | |
| Race: | | | | |
| Unknown or Not Reported: | | | | |

If unknown, please explain why:

Indicate the categories of subjects and controls to be included in the study. You may be required to complete additional forms depending on the subject categories which apply to your research. If the study does not involve direct intervention or direct interaction with subjects, (e.g., record-review research, outcomes registries), do not check populations which the research does not specifically target. For example: a large record review of a diverse population may incidentally include a prisoner or an international citizen, but you should not check those categories if the focus of the study has nothing to do with that status.

Check All That Apply (at least one item must be selected)

ADDITIONAL INFORMATION:

- Children (individuals under age 18)
- Wards of the State (Children)
- Emancipated Minors
- Students
- College of Medicine Students

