This study is designed as a randomized control trial. Figure 1 shows the time line for the study. There will be four groups of subjects, (1) normal weight-bearing with massage (WB-M), (2) normal weight bearing without massage (WB-C) (3) ULLS, no massage (control, U-C), and (4) ULLS with massage (U-M). We expect to recruit 140 subjects to in order in fully enroll 128 (32 per group, n = 3 per group for attrition). For measurement of protein synthesis, participants will ingest three 50 mL doses of heavy water (2H2O) for the first two days and the dose will decrease to two 50 mL doses per day (a total of 1000 mL of heavy water for each subject over the course of the trial). 3-4 blood draws will be taken on days 2, 5, 7, and 9 and each will be drawn at the same time each day. Subjects in U-C and U-M groups will have their left leg immobilized and suspended using a hinged knee brace. Those immobilized will be required to wear the brace and use crutches at all times, except while showering and sleeping. Immobilization will begin on day 2 and will continue until the end of the study (day 9). Members of the research team will use a custom-made device to massage the quadriceps region of subjects' left leg and leave the right leg unaffected in the WB-M and U-M groups. Massage treatments will begin on day 3 and will take place every other day (day 5, 7, 9) until the end of the study. A baseline muscle biopsy of the vastus lateralis will be taken from the right leg on day 2, prior to the first massage. Muscle biopsies will then be taken from both legs 4-6 hours after the last massage on day 9, and the muscle tissue will be frozen for further examination. (See Figure 1). Sham treatment for the WB-C and U-C groups will include us touching the skin using a light brushing technique.

For the weight bearing groups as comparison groups, they will also have to drink deuterium oxide heavy water over 9 days which is associated with 3-4 blood draws but will not have to wear a brace or use crutches. Weight bearing control groups will only have one biopsy taken on day 9 while weight bearing massage groups will have two biopsies taken (day 2- right leg, and day 9- left massaged leg). This will still allow for effective comparison between groups and will reduce burden on these participants. We will enroll the weight bearing groups after immobilization groups to ensure that those interested in the study will not drop out after possible randomization into the immobilization group.

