Outreach activities: The CCTS attends outreach activities to promote research participation in general (e.g., Roots & Heritage Festival, Latino Festival, Eastern Kentucky University, Transylvania Health fairs, etc.) and will bring all relevant study flyers that are enrolling participants.

Attachments

| Attach Type | File Name |
|-------------|--|
| Advertising | REHAB-191 MON[1] MP edit APPROVED.pdf |
| Advertising | REHAB-191_flyerAPPROVED.pdf |
| Advertising | REHAB-191_ResearchMatch email APPROVED.pdf |
| Advertising | REHAB-191_SocialMedia APPROVED.pdf |

Research Procedures

Describe how the research will be conducted.

- What experience will study participants have?
- What will study participants be expected to do?
- How long will the study last?
- Outline the schedule and timing of study procedures.
- Provide visit-by-visit listing of all procedures that will take place.
- Identify all procedures that will be carried out with each group of participants.
- Describe deception and debrief procedures if deception is involved.

Differentiate between procedures that involve standard/routine clinical care and those that will be performed specifically for this research project. List medications that are explicitly forbidden or permitted during study participation.

Cyclic Compressive Loading (CCL) Device Reliability and Validity Testing:

Forty participants will be requested to participate in pilot testing of the CCL device. This testing will be used to validate the equipment. Two different clinicians will massage all participants for 15 minutes on two separate days. The load applied to the tissue will be measured and compared between clinicians and days. This will allow analysis of inter-rater reliability and test-retest reliability. The same inclusion and exclusion criteria for the participants will be used as in the original study.

Medical Health Questionnaire:

Potential subjects will be verbally screened to see if they are eligible for this study.

Heavy Water:

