## Statistical Design and Power

Statistical Analysis. The College of Health Sciences supports the effort of a biostatistician through the Office of Research to provide dedicated support to funded investigators. All statistical analyses will be performed using SAS© 9.4 (SAS institute, Cary NC). The sample size calculations herein have been performed with the assistance of the biostatistician. We used 4 main outcomes to determine sample size: cross sectional area (CSA), myofibrillar protein synthesis (MyoKsyn), extracellular vesicle (EV) number and mRNA levels of Rab27. These outcomes were also measured in the pilot study we performed with 6 subjects and the variance and expected differences were based on the data from the pilot study. See Table below.

% change	EV number	CSA	MyoKsyn	Rab27 mRNA
Pilot study data	0.29	6.1	36	116
Expected μ₁-μ₂	0.29	10	70	150
Standard Deviation, σ	0.294	11	76	170
Effect Size, $\delta =  \mu_1 - \mu_2 /\sigma$	0.99	0.91	0.92	0.88
n per Group	18	21	19	22

From this sample size analysis we decided to use n=22 per group, because it would give us the power to determine differences in the mRNA expression of EV biogenesis markers as well as enough power to detect changes in muscle size and protein synthesis. To determine statistically significant differences between the groups we will use a Two Way ANOVA to determine effects of ULLS and massage. Holm Sidak posthoc tests will be performed in case significance is seen with the ANOVA. We will use an unpaired t-test to test for cross over effect (UM versus UC left nonmassaged limb).

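### The SAP adopts 22 per group (88 in all) and the protocol states 32 per group (128 enrolled, 140 recruited); no text shown derives 32 or reconciles the two

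*Protocol*

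**What the plan says.** Five statements bear on the size of the trial.

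- SAP, Statistical Design and Power: four outcomes give 18, 21, 19 and 22 per group, and the largest is adopted: "From this sample size analysis we decided to use n=22 per group, because it would give us the power to determine differences". No alpha or power value is stated.
- Protocol, Research Description, Study Design: after naming the four groups, "We expect to recruit 140 subjects to in order in fully enroll 128 (32 per group, n = 3 per group for attrition".
- Protocol, description of the subject population: "This study will include 70 subjects of either gender. Subjects will be randomly assigned to the following groups", followed by the same four groups.
- Protocol, planned-enrolment table in the same section, under the instruction "Indicate the targeted/planned enrollment of the following members of minority groups and their subpopulations": men 3 + 9 + 2 + 56 and women 3 + 9 + 2 + 56.
- Protocol, Research Procedures, device reliability and validity testing: "Forty participants will be requested to participate in pilot testing of the CCL device". These people receive massage only: "Two different clinicians will massage all participants for 15 minutes on two separate days". The text does not say whether they count within the 128 or the 140.

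**The concern.** The two documents give different sizes for the same four randomised groups, and both figures stand intact in running text. The per-group size decides how many healthy volunteers are randomised and biopsied. It also decides whether the SAP's power statement describes the trial being run. The protocol classes the study as greater than minimal risk and ties its monitoring board to the biopsies, so unexplained extra biopsies matter. A reader holding both documents cannot tell which size applies, or where enrolment to the four groups should stop.

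**Working it through.** **1. Reproduce the SAP's figure.** Inputs are the expected differences and standard deviations in the SAP table. Alpha and power are not stated, so I assume a two-sided 5% two-sample t-test. Effect size d = difference / SD. The required n is the smallest per-group size at which the noncentral t power (df = 2n - 2, noncentrality d x sqrt(n/2)) reaches the target.

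| Outcome | d | SAP n | n, 80% | n, 90% | n, 95% |
|---|---|---|---|---|---|
| EV number | 0.29/0.294 = 0.986 | 18 | 18 | 23 | 28 |
| CSA | 10/11 = 0.909 | 21 | 21 | 27 | 33 |
| MyoKsyn | 70/76 = 0.921 | 19 | 20 | 26 | 32 |
| Rab27 mRNA | 150/170 = 0.882 | 22 | 22 | 28 | 35 |

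At 80% power the adopted maximum of 22 is reproduced; only MyoKsyn differs, by one. The table does not identify the settings uniquely: one-sided 5% with 90% power by normal approximation gives 18, 21, 21 and 22.

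**2. Can the same inputs give 32 as the adopted maximum?** Not at 80%, 90% or 95% power, where the maxima are 22, 28 and 35. At 32 per group the Rab27 comparison has 93.5% power, which is not a target that either document names. Splitting alpha over four outcomes (0.0125 each, 80% power) gives a maximum of 31, again not 32, and the SAP describes no such split.

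**3. Does attrition bridge the gap?**
- 22 + 3 = 25 per group, and 4 x 25 = 100, which is neither 128 nor 140.
- Inflating 22 to 32 would need a loss of 1 - 22/32 = 31%. The stated 3 per group is 3/25 = 12% or 3/35 = 8.6%.

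**4. Totals under each reading.**
- Protocol sentence alone: 4 x 32 = 128 and 4 x (32 + 3) = 140. It closes.
- SAP size with the 40 device-testing participants: 88 + 40 = 128 and 88 + 12 + 40 = 140. This also closes, provided the 12 for attrition is included in the second sum.
- Planned-enrolment table: 70 men + 70 women = 140. This fits either reading.
- 70 randomised to four groups: 70/4 = 17.5 per group. This fits neither 22 nor 32.

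**5. Biopsies in completers.** Under Study Design, the immobilised groups have one biopsy on day 2 and two on day 9, so three each. For the others, "Weight bearing control groups will only have one biopsy taken on day 9 while weight bearing massage groups will have two biopsies taken". The sum over one person per group is 3 + 3 + 2 + 1 = 9.
- At 22 per group: 22 x 9 = 198.
- At 32 per group: 32 x 9 = 288.
- Difference: 90 biopsies, in 4 x 10 = 40 more volunteers.

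The payment section agrees with three biopsies in the immobilised groups: 4 x $15 + 3 x $50 + $100 + $65 = $375.

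**The case against.** The protocol sentence is arithmetically sound by itself, and 32 is above every requirement in the SAP table, so enrolling 32 cannot underpower the SAP's stated comparison. Both points stand. They do not remove the conflict: the SAP says 22 was decided on, and nothing shown explains the further 10 per group.

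Some totals may also have been given in places not available here. The form's fields for the maximum number of subjects and the approved estimate are blank in the text shown, and some pages were removed. I therefore say only that no text shown derives 32. Blank fields for an overall total would not make 22 and 32 agree.

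Three stronger readings are tempting, and the documents do not support them.
- A reader might infer that 32 is simply 128/4 with the 40 device-testing participants folded in. The sums fit, but no sentence links the 40 to 128 or 140. The second match is not independent evidence either, because both readings add the same 12, and the table total of 140 does not discriminate.
- A reader might infer that the 70 means 70 of each sex and should be changed to 140. As written it is the number assigned to the four groups. If 22 is meant, only 100 would be recruited to those groups, so rewording it to 140 would prejudge the answer.
- A reader might infer that 22 is too small once the post hoc tests are adjusted ("Holm Sidak posthoc tests will be performed in case significance is seen with the ANOVA"). That depends on alpha, sidedness and the number of comparisons, none of which is stated. The missing detail belongs in the derivation but is not in itself evidence that 22 is inadequate.

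**Conclusion.** The conflict holds. The SAP's 22 per group (88) and the protocol's 32 per group (128 enrolled, 140 recruited) cannot both be the randomised size, so one document is wrong as written. The stated attrition does not explain the gap, and the SAP's inputs do not lead to 32 at the usual power targets under an assumed two-sided 5%. The documents do not show which figure is intended.

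The consequence depends on the answer. If 32 is meant, 40 more volunteers and 90 more biopsies go beyond the size that the SAP justifies. If 22 is meant, the protocol misstates its per-group size. The biopsy count assumes equal groups and that every completer has every scheduled biopsy. The direct conflict between 22 and 32 rests on no assumption about alpha or power.

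**What to change.** - State one randomised per-group size in both documents and correct whichever of the two figures is wrong.
- Give the derivation that supports the chosen size, including the test, alpha, sidedness and power.
- Put attrition and the 40 device-testing participants on separate lines, and say whether the 40 lie inside 128 and 140.
- Reconcile the 70 in the subject description and the 140 in the planned-enrolment table with the chosen size, without assuming in advance what either was meant to count.

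The cost is wording plus one sample-size statement. If 22 is meant, 4 x 25 + 40 = 140, the recruitment total already stated, so no participants are added. If 32 is meant and the 40 are additional, recruitment is 140 + 40 = 180, and the planned-enrolment table would have to say whether it covers them.

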The unilateral lower limb suspension (ULLS) method has been recently developed to mimic the 0-g conditions in space and assist in assessing the efficacy of interventions to combat muscle atrophy and facilitating in-vivo muscle performance studies.¹⁰ ULLS has been shown to mimic bed rest and is a valid technique.¹¹ Just as muscle tissue responds to loading, muscle responds to unloading as well. Unloading a muscle can result in muscle atrophy at a weekly rate of about 2.5% particularly for knee extensors.¹⁰ Short term ULLS (10-16 days) doesn't seem to result in large macroscopic changes in muscle size or CSA but individual muscle fiber size has been shown to decrease at a weekly rate that varies between 3-8% across different studies.¹⁰ In specific studies, increased markers for muscle proteolysis were found after 3 days of ULLS¹⁰ and protein synthesis rate appeared to decrease after 10 days of ULLS.⁹ ULLS is a well-accepted model for disuse-induced muscle atrophy.¹⁰ There are few systemic or general deconditioning effects that have been discovered from incorporating ULLS into research procedures.¹⁰ Overall, ULLS has been shown to be a valid, practical, and cost-effective method to induce atrophy and study the effects on skeletal muscle.¹⁰

Objectives

List your research objectives. Please include a summary of intended research objectives in the box below.

The objective of this study is to determine if an optimal load of massage induces protein synthesis and increases cross sectional area

in unperturbed or atrophied human skeletal muscle tissue. In addition, we will determine whether an optimal load induces muscle damage and causes a satellite cell response in control and atrophied human skeletal muscle tissue while also examining extracellular vesicles and their possible role in a physiological phenomenon called the crossover effect. We hypothesize that 15 min of massage with a 35 N load for 4 days will not induce muscle damage but will still cause an increase of satellite cells, extracellular vesicles, as well as in cross sectional area and protein synthesis.

Study Design

Describe and explain the study design (e.g., observational, secondary analysis, single/double blind, parallel, crossover, deception, etc.).

- *Clinical Research*: Indicate whether subjects will be randomized and whether subjects will receive any placebo.

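### The SAP does not say how day-2 muscle enters the analysis; the weight-bearing control group has none, and the crossover test names a limb that is massaged in U-M

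*Protocol*

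**What the plan says.** **Biopsies (Protocol, Research Description, Study Design).** The general schedule reads "A baseline muscle biopsy of the vastus lateralis will be taken from the right leg on day 2, prior to the first massage" and "Muscle biopsies will then be taken from both legs 4-6 hours after the last massage on day 9". The weight-bearing groups are then cut back: "Weight bearing control groups will only have one biopsy taken on day 9 while weight bearing massage groups will have two biopsies taken". The two WB-M biopsies are the right leg on day 2 and the massaged left leg on day 9. The text does not state the leg for the single WB-C biopsy; Figure 1, which is not visible here, may show it. Massage is applied to the "left leg and leave the right leg unaffected in the WB-M and U-M groups".

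**Analysis (SAP, Statistical Design and Power).** For the four groups, "we will use a Two Way ANOVA to determine effects of ULLS and massage", and "Holm Sidak posthoc tests will be performed in case significance is seen with the ANOVA". For the crossover effect, "We will use an unpaired t-test to test for cross over effect (UM versus UC left nonmassaged limb". No baseline covariate, change score or repeated-measures term is named, and neither the response nor its time point is defined. The sizing table is labelled as percent change, without saying from what.

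**Objective (Protocol, Objectives).** The effect of massage is to be studied "in unperturbed or atrophied human skeletal muscle tissue", so the weight-bearing comparison is part of the question.

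**The concern.** Three things are left open or do not fit together.

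- **Response.** The only scale in the SAP is percent change. If that means change from the subject's own day-2 biopsy, one of the four groups cannot supply it, and the half of the objective on unperturbed muscle is lost for biopsy outcomes.
- **Day-2 tissue.** Both suspension arms give a biopsy before any massage. It is a legitimate covariate for U-M versus U-C, and the SAP gives it no stated role. Depending on the response meant, the crossover test either ignores it or uses it through a less efficient change score.
- **Limb.** A crossover effect is an effect in a limb that was not massaged. The SAP places that limb on the left. In U-M the left leg is massaged, so the test as worded has no matching limb in that arm.

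**Working it through.** I take CSA and Rab27 mRNA to be biopsy outcomes. EV number is left aside, because blood is drawn on day 2 and a blood-based measure would not have the same gap.

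**1. The plan's own sample sizes.** A two-sample t-test with two-sided 0.05 and 80% power (both assumed; the SAP states neither) and effect sizes 0.29/0.294 = 0.986, 10/11 = 0.909, 70/76 = 0.921 and 150/170 = 0.882 gives 18, 21, 20 and 22 per group. The SAP has 18, 21, 19 and 22. The sizing is thus a plain two-group comparison, with no separate allowance for a baseline covariate.

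**2. Which responses exist.**

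| Group | Day 2 | Day 9 | Change from day 2 | Day-9 left minus right |
|---|---|---|---|---|
| U-M | right | left, right | yes | yes |
| U-C | right | left, right | yes | yes |
| WB-M | right | left | yes, across legs | no |
| WB-C | none | one, leg not stated | no | no |

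The Payment section agrees with 3, 2 and 1 biopsies at \$50 each: 4×15 + 3×50 + 100 + 65 = \$375; 15 + 2×50 + 65 = \$180; 15 + 50 + 65 = \$130.

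**3. The ANOVA.** With columns for intercept, suspension, massage and interaction, the design matrix has rank 4 when all cells are filled and rank 3 without WB-C. On change from day 2, the interaction and WB-M versus WB-C cannot be estimated; U-M versus U-C can. On a day-9 value, everything can.

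**4. Does the table SD fit a day-9 response?** If the tabled SD is that of change from day 2, and day-2 and day-9 variances are equal, then day-9 SD = table SD / √(2(1−r)). With the expected difference unchanged and n = 22, the power of an unadjusted day-9 comparison would be:

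| r (assumed) | CSA | Rab27 mRNA |
|---|---|---|
| 0.3 | 93.6% | 92.3% |
| 0.5 | 83.8% | 81.6% |
| 0.7 | 62.6% | 60.1% |

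**5. Gain from ANCOVA in U-M versus U-C.** The documents give no correlation r between day-2 and day-9 values, so r is assumed. ANCOVA variance relative to a day-9 comparison is (1−r²)(1 + 1/(2n−4)). At n = 22 the second factor is 1 + 1/40 = 1.025. Interval width also carries the critical values, 2.0195 on 41 df and 2.0181 on 42 df. The combined constant is 1.025 × (2.0195/2.0181)² ≈ 1.026.

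- Against a day-9 t-test, the squared width ratio is (1−r²) × 1.026.
- Against a change-from-day-2 t-test with equal variances, the comparator variance is 2(1−r), so the ratio is (1+r)/2 × 1.026. This is for absolute change; percent change would follow it only approximately.

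| r (assumed) | Ratio, day-9 | Interval narrower by | Ratio, change | Interval narrower by |
|---|---|---|---|---|
| 0.3 | 0.934 | 3.4% | 0.667 | 18% |
| 0.5 | 0.770 | 12.3% | 0.770 | 12% |
| 0.7 | 0.523 | 27.6% | 0.872 | 7% |

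Against the day-9 t-test, break-even is at r ≈ 0.16, and at r = 0 the ANCOVA interval is √1.026 − 1 = 1.3% wider. Against the change score, ANCOVA loses only when (1+r)/2 × 1.026 exceeds 1, that is at r above about 0.95. At the Protocol's 32 per group, the day-9 figures are 3.8%, 12.7% and 28.0%. A simulation at n = 22 with normal data gave a type I error of 0.050 to 0.053 for the ANCOVA.

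**6. The limb.** The SAP sets the crossover test in a left limb that is not massaged. Such a limb exists in U-C, where the left leg receives sham. In U-M the Protocol massages the left leg and leaves the right alone.

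**The case against.** **The day-2 tissue may be in use already.** A reader might infer that the stated analyses discard the day-2 biopsies. The documents do not support that. The response is undefined, the only scale is percent change, and the crossover t-test could be run on change from day 2, which both suspension arms can supply. What stands is that the SAP does not say whether or how this tissue enters.

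**Percent change may mean something else.** It could be relative to a control-group mean, which fills every cell. The Protocol presents the reduced weight-bearing biopsies as deliberate and as still permitting group comparisons, and on a day-9 response that is right. So the four-group ANOVA is not unworkable; it fails only on a response that needs day-2 tissue from WB-C.

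**This is efficiency, not bias.** That is correct for U-M versus U-C. Under randomisation the unadjusted comparison is valid, and the gain rests on an unstated r. For the left leg the covariate comes from the other leg, where r may be lower.

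**The ANCOVA could be pushed further.** One could put its p-value into the Holm-Sidak set. I would not. Those tests run only after a significant ANOVA, and a two-arm adjusted p-value would sit beside contrasts from a four-group model.

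**Conclusion.** Two statements rest on the text alone. Change from day 2 cannot be computed in WB-C, so a four-group ANOVA of a muscle outcome on that response cannot estimate the interaction or the weight-bearing massage effect. And the crossover limb in the SAP does not match the Protocol's massage allocation in U-M.

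The case for ANCOVA is one of precision. It rests on random assignment between U-M and U-C, on a covariate taken before massage, and on an assumed r. Whichever t-test was meant, the interval narrows by between 3% and 28% for r from 0.3 to 0.7 at 22 per arm, with a small loss at very low r (day-9 t-test) or at r close to 1 (change score). I rate this a cheap improvement, with the limb wording wrong as written. Confidence is moderate, because the SAP leaves the response undefined.

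**What to change.** 1. State that the four-group ANOVA of muscle outcomes uses the day-9 value, from the same leg in every group, and name the leg of the WB-C biopsy. Confirm that the table SDs are on that scale; if they are SDs of change, redo the sizing.
2. Reconcile the crossover limb with the Study Design section. For CSA and Rab27 mRNA, replace the unpaired t-test by ANCOVA of the day-9 value on the day-2 right-leg value, with arm as the factor. If the crossover limb is the right leg, this is a same-limb baseline.
3. Report the same adjusted analysis for the left-leg U-M versus U-C comparison as a pre-specified supporting estimate, noting that day 2 is there a contralateral covariate. Leave the ANOVA-gated Holm-Sidak set unchanged.
4. Leave MyoKsyn out of the ANCOVA unless the SAP states that day-2 tissue does not enter its calculation.

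The cost is SAP wording and one degree of freedom per ANCOVA. No further biopsy is needed. The weight-bearing comparison stays unadjusted for baseline, and precision falls slightly if r proves very low.
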